2 ELIGIBILITY ASSESSMENT AND ENROLLMENT

2.1 ELIGIBILITY CRITERIA

2.1.1 Inclusion Criteria

- 2.1.1.1 Patients must have histologically confirmed solid tumor malignancy for which no curative therapy exists.
- 2.1.1.2 Pancreatic adenocarcinoma, extrahepatic cholangiocarcinoma or epithelioid subtype of mesothelioma, as determined by NCI Laboratory of Pathology, OR for all other tumor types, at least 20% of tumor cells must express mesothelin. Determination can be made using archival tumor tissue or fresh biopsy if archival tumor tissue is not available.
- 2.1.1.3 All patients must have evaluable disease (i.e. measurable per RECIST 1.1. or by following CA19-9 tumor marker). Patients in the expansion cohort must have measurable disease, per RECIST 1.1. See Section 6.3 for the evaluation of measurable disease.
- 2.1.1.4 Patients must have received at least one prior standard systemic treatment regimen for advanced disease OR be ineligible to receive available standards due to co-morbidities, prior toxicity, lack of standard options for tumor type, or having received all standards

available for prior treatment of early stage disease OR have refused first-line standard systemic treatment but have received prior anti-cancer treatments.

- 2.1.1.5 Patients with dMMR/MSI-H disease must have received at least one prior anti-PD1 therapy, be ineligible to receive this treatment due to concurrent medical conditions, or have refused this therapy.
- 2.1.1.6 ECOG performance status (PS) 0-2 (Appendix A- Performance Status Criteria).
- 2.1.1.7 Age ≥18 years. Because no dosing or adverse event data are currently available on the use of LMB-100 alone or in combination with tofacitinib in persons with <18 years of age, children are excluded from this study.
- 2.1.1.8 Patients must be more than 14 days removed from most recent minor surgical procedure (such as biliary stenting), 28 days from most recent major surgical procedure and 14 days from radiation therapy, systemic treatments (such as chemotherapy), or experimental drug treatment. All acute toxicities from prior treatment must have resolved to grade 1 or less except alopecia, anemia, peripheral neuropathy, or endocrinopathies corrected by replacement therapy.
- 2.1.1.9 Adequate hematological function: neutrophil count of $\ge 1.5 \times 10^3$ cells/µL, platelet count of $\ge 85,000/\mu$ L, hemoglobin ≥ 9 g/dL
- 2.1.1.10 Serum albumin \geq 2.5 mg/dL without intravenous supplementation

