2.2.2 Screening activities performed after a consent for screening has been signed

For patients requiring testing for MSLN expression (see Section 2.3.1), screening will occur on this study. For all other subjects, screening will occur on study 01-C-0129.

The following activities will be performed only after the subject has signed the appropriate consent for screening. They will be performed within 28 days before registration for study treatment unless specified:

- Assess tumor MSLN expression by immunohistochemistry analysis in archival tissue or fresh biopsy samples ONLY for patients who do not have a diagnosis of epithelioid mesothelioma, extrahepatic cholangiocarcinoma or pancreatic adenocarcinoma.
- Medical History and physical exam
- Vital signs including ambulatory oxygen saturation by pulse oximetry
- ECOG performance status
- Pregnancy test in women of childbearing potential (within 7-days prior to initiation of study therapy)
- ECG
- Echocardiogram
- CT scan of chest, abdomen and/or pelvis and areas of known or suspected disease involvement; MRI and/ or PET scan may also be performed when appropriate per PI discretion.
- CBC with differential, Acute Care Panel (sodium, potassium, chloride, bicarbonate, creatinine, glucose, BUN), Hepatic Panel (alkaline phosphatase, AST, ALT, total bilirubin, direct bilirubin), Mineral Panel (albumin, calcium, magnesium, phosphorus), creatine kinase, C-reactive protein, 1,25-dihydroxy vitamin D, Coagulation (PT, PTT), lactate dehydrogenase
- CA 19-9 serum tumor marker for pancreatobiliary cancer patients, or other appropriate tumor marker in other tumor types
- Testing for HIV, HCV, HBV: anti-HIV antibody, Anti-HCV Antibody, HBs Ag Screening
- Screening for latent tuberculosis by interferon-x release assay: QuantiFERON-TB Gold Plus or similar
- Urinalysis

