3.1.3 Treatment Extension

Participants who complete 3 cycles of therapy with LMB-100/tofacitinib and appear to be deriving clinical benefit as evidenced by lack of progression on CT scan and decreasing serum tumor marker (in patients with serum tumor marker that has historically followed their disease trend) may continue to receive additional cycles of treatment at the discretion of the PI until unacceptable toxicity or patient is no longer thought to be benefiting, or PI's decision to discontinue treatment. If a participant is offered treatment extension but refuses, he/she will be removed from protocol therapy. Participants offered treatment extension may defer immediate treatment with study drugs to take a treatment holiday or to receive other intervening treatments (including investigational treatments). If a participant chooses to defer treatment extension beyond 6 weeks or to have a different intervening therapy, the PI may require to repeat some screening safety evaluations before reinitiating LMB-100/tofacitinib and will require washout periods and criteria consistent with those described in Sections 2.1.1.8, 2.1.1.9 and 2.1.1.10. Safety monitoring while receiving treatment extension will continue as described in the Study Calendar. Limited research labs will be taken as described in Sample Collection Schedule (Section 5.2).

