3.4 STUDY CALENDAR

Unless otherwise specified, screening assessments must occur within 28 days prior to registration for study treatment. Cycle 1, day 1 assessments may occur up to 7 days prior to treatment initiation. If screening tests were performed within this window, then they do not need to be repeated on C1D1. Dosing cycles may be delayed for up to one week or started up to 2 days early to accommodate schedule conflicts, federal holidays and inclement weather, etc. They may be delayed for up to two weeks due to toxicity. There is no time limit on dosing cycle delays for patients receiving treatment extension.

			All Cycl	es (21 da	ys)					Post T	herapy
Procedure	Screening	Day 1	Day 3*	Day 4	Day 6	Day 8	Day 9	Day 15	Day 21	Safety Follow Up Visit ⁷	Long Term Follow Up ¹¹
Tofacitinib		ad	ministered	BID days	1-10 of ea	ach cycle					
Prophylactic anti- coagulation		Khorana Score < 2: administer daily on days 1-11 of each cycle Khorana Score ≥ 2: administer throughout treatment until 14 days after last dose of tofacitinib/ LMB-100									
LMB-100				Х	Х	Х					
History and PE	Х	C1 only	Х		Х	Х				Х	
Weight			Х		Х	Х	C1 only			Х	
Height			C1 only								
Vital signs ¹	Х	C1 only	Х	Х	Х	Х	C1 only			Х	
ECOG Performance Status	X	C1 only	X							Х	
Labs ²	X	C1 only	X		Х	Х		C1 only ¹⁴	C1 only ¹⁴	Х	
D-dimer		C1 only	Х			Х					
Cholesterol Panel		C1 only								Х	
TBNK		C1 only	C1 and C3 only				C1 only				
1,25-dihydroxy Vit D	Х									Х	

Abbreviated Title: LMB100 + *tofacitinib in PDA Version Date:* 08/19/20

			All Cycl	es (21 da	ys)					Post T	herapy
Procedure	Screening	Day 1	Day 3*	Day 4	Day 6	Day 8	Day 9	Day 15	Day 21	Safety Follow Up Visit ⁷	Long Term Follow Up ¹¹
Hepatitis and HIV screening panel	Х										
IGRA	Х										
Urinalysis	Х		Х		Х	Х				Х	
Urine albumin and creatinine	C1 only		C1 only		C1 only	C1 only					
Pregnancy test ³	Х		Х								
Confirmation of Dx ⁴	Х										
Assessment of tumor MSLN expression ^{4, 5}	X										
CT CAP and/or MRI ⁸	X	•	cles of stud	•		days				Х	Х
CA 19-9-or appropriate tumor-specific marker ⁵			Х							X	
Doppler U/S of bilateral lower extremities		Optional ¹⁵									
ECG	X		C1 only			C1 only				X	
Echocardiogram	Х										
Ambulatory Oxygen Saturation	Х										
Chest X-ray			X ⁹								
NIH Advance Directives Form ⁶		C1 only ⁶									
Biopsy	X ¹³	C1 only ¹²	C2 only 12								

Abbreviated Title: LMB100 + tofacitinib in PDA *Version Date:* 08/19/20

			All Cycl	es (21 da	ys)					Post T	herapy

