Procedure	Screening	Day 1	Day 3*	Day 4	Day 6	Day 8	Day 9	Day 15	Day 21	Safety Follow Up Visit ⁷	Long Term Follow Up ¹¹
PKs		Please refer to Section 5.2									
Correlative Studies		Please	refer to Sec	ction 5.2							
Annual phone call to monitor survival and additional CA therapy											Х
Adverse events ¹⁰		Monitored continuously									
Concomitant meds		Monitored continuously									

*If not performed on day 3, may be performed on day 4 prior to the start of LMB-100 infusion

- Vital signs including temperature, blood pressure, pulse rate, and oxygen saturation should be recorded on the indicated days. In addition, systolic blood pressure, pulse rate, and oxygen saturation must be monitored pre-infusion, every 15 minutes (± 5 minutes) during the infusion, at end of infusion (EOI), then 30, 60 and 120 minutes (±15 minutes) following EOI.
- ² CBC with differential, Acute Care Panel, Hepatic Panel, Mineral Panel, C-reactive protein (CRP), Creatine Kinase (CK), PT, PTT, LDH. PT and PTT will be done only at the time of screening, Day 1 of each cycle, and within 24hrs prior to biopsies (if biopsy will be performed).
- ³ Pregnancy test required in women of childbearing potential; i.e. premenopausal women and women ≤ 2 years after menopause (menopause is defined as amenorrhea for > 2 years)
- ⁴ Assessment may occur at any time prior to enrollment
- ⁵ Applicable only to patients on dose escalation with tumor types other than pancreatic adenocarcinoma, extrahepatic cholangiocarcinoma, or epithelioid subtype of mesothelioma
- ⁶ As indicated in Section **11.3**, all subjects will be offered the opportunity to complete an NIH advanced directives form. This should be done preferably prior to beginning treatment but can be done at any time during the study as long as the capacity to do so is retained. The completion of the form is strongly recommended but is not required.
- ⁷ Safety follow up will occur 3 6 weeks after last dose of study therapy. If the patient is unable to return to the clinic for the follow up visit, an adverse event assessment will be performed by telephone.

- ⁸ Scans, every ~9 weeks, will only be performed until disease progression. Note: for patients on long term follow up, scans may be performed outside of NIH. Gadolinium will be used for MRI in patients where MRI is required.

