10.4.9 Exploratory Analyses

The following are the intended exploratory analyses focusing on the patients in the expansion cohort:

Disease control rate (DCR) at 9 weeks will be estimated along with a 95% confidence interval. PFS and OS will be estimated by the Kaplan-Meier method, along with 95% confidence intervals. Changes in appropriate tumor markers with treatment (if applicable to patient's tumor type) will be determined and tested for change from baseline using a Wilcoxon signed rank test. Titer of free anti-LMB-100 antibodies at the start of each cycle and following completion of treatment will be obtained and results reported descriptively; the relationship of these values with peak serum drug levels of LMB-100 will be explored. Association of response with tumor MSLN expression will be done by comparing levels between responders and non-responders using an appropriate nonparametric test such as a Cochran-Armitage test or Fisher's exact test. Changes in circulating endothelial cells following immunotoxin treatment, changes in serum cytokines following immunotoxin treatment, and changes in tumor microenvironment following immunotoxin treatment will be reported descriptively, with statistical testing of changes as appropriate. Any statistical tests performed on the exploratory endpoints will have results presented without formal adjustment but interpreted in the context of the number of tests performed. In patients receiving treatment extension, the anti-drug antibodies and peak plasma LMB-100 drug levels will be obtained at each cycle after cycle 3 and reported with descriptive statistics. The levels of these

measures after cycle 3 may be compared descriptively to those in earlier cycles for purposes of evaluating the effect of the agent in this small subset of patients.

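### The mesothelin-testing footnote is also attached to the tumour-marker row of the Study Calendar; read literally, it leaves the expansion cohort with no scheduled follow-up marker for the change test in 10.4.9

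*Combined protocol and SAP*

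**What the plan says.** The Study Calendar (3.4) lists a row "CA 19-9-or appropriate tumor-specific marker ⁵". It is marked on Day 3 of all cycles and at the Safety Follow Up Visit, and its Screening cell is empty. An asterisk on the Day 3 column lets those assessments move to Day 4 before the LMB-100 infusion. Footnote 5 reads "Applicable only to patients on dose escalation with tumor types other than pancreatic adenocarcinoma, extrahepatic cholangiocarcinoma, or epithelioid subtype of mesothelioma". The same footnote sits on the mesothelin-expression row, where it agrees with 2.2.2.

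The marker is used in these places:

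- 2.2.2 requires at screening "CA 19-9 serum tumor marker for pancreatobiliary cancer patients, or other appropriate tumor marker in other tumor types".
- 10.4.9, which is focused on the expansion cohort, says that marker changes "will be determined and tested for change from baseline using a Wilcoxon signed rank test".
- 3.1.3 makes extension beyond three cycles depend in part on "decreasing serum tumor marker (in patients with serum tumor marker that has historically followed their disease trend".
- 6.3.3.2 requires an initially raised marker to normalise before a complete response is called.
- 10.3.3 counts a marker increase in the non-target response assessment.
- 2.1.1.3 accepts disease that is "measurable per RECIST 1.1. or by following CA19-9 tumor marker" as evaluable, but expansion patients must have measurable disease.

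**The concern.** Under 2.1.1.15 an expansion patient must have pancreatic adenocarcinoma or extrahepatic cholangiocarcinoma. The footnote therefore excludes each of them twice, by cohort and by tumour type. It also excludes escalation patients with those two cancers or with epithelioid mesothelioma. A row named for CA 19-9 would then leave out the patients for whom 2.2.2 names CA 19-9.

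A signed-rank test of change needs a baseline and a later value in the same patient. If the calendar is followed to the letter, the later value is not scheduled in the cohort for which the test is written. Any values obtained anyway would be unscheduled. Their timing would vary and could depend on how the patient was doing, which is a poor basis for a paired comparison. The extension, complete-response and non-target-response provisions would also have no scheduled marker behind them in these patients.

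**Working it through.** The plan states no figure for the marker analysis, so the check is a trace of the schedule followed by a count.

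**1. Could another provision supply a follow-up marker?**

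- Routine labs (3.4, footnote 2): blood count, chemistry panels, CRP, CK, coagulation and LDH. No tumour marker.
- Sample Collection Schedule (5.2): drug levels, ADA, cytokines, circulating endothelial cells, immune assays and tissue. No tumour marker.
- Screening (2.2.2): a marker, but before treatment only.
- Long-term follow-up column (3.4): no mark on the marker row.
- 3.1.3, 6.3.3.2, 10.3.3 and 10.4.9: all use marker values, but none sets a day.

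The calendar row is therefore the only source of a scheduled post-screening value.

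**2. Who keeps the Day 3 and safety-visit draws?** Two readings of the footnote are possible. The literal one applies it to the whole row. The narrow one applies it only to the substitute marker, the words just before the superscript.

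| Patients | Literal | Narrow |
|---|---|---|
| Expansion (pancreatic or extrahepatic biliary) | none | CA 19-9 kept |
| Escalation, same two cancers | none | CA 19-9 kept |
| Escalation, epithelioid mesothelioma | none | none |
| Escalation, other tumour types | kept | kept |

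Under the narrow reading, epithelioid mesothelioma still loses its marker. It is not a pancreatobiliary cancer, so 2.2.2 assigns it a substitute marker, and the footnote excludes it from the substitute.

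**3. Scheduled values for one expansion patient completing three cycles.**

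- Literal reading: 1 screening + 0 Day 3 + 0 safety visit = 1 value. Scheduled baseline/follow-up pairs: 0 of 15.
- Footnote removed from the row: 1 screening + 3 Day 3 + 1 safety visit = 5 values, of which 5 − 1 = 4 come after screening. Scheduled pairs: up to 15 of 15.

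The four post-screening values are not equivalent. LMB-100 starts on Day 4 and tofacitinib on Day 1, so the cycle 1 Day 3 draw comes after tofacitinib has started but before any LMB-100. The values after LMB-100 number 4 − 1 = 3: Day 3 of cycles 2 and 3, and the safety visit. Footnote 7 allows the adverse event assessment by telephone if the patient cannot return, so the safety-visit draw may be missed.

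**4. Is the primary analysis touched?** No. The expansion rule in 10.2 uses serum drug levels. Its stated figures reproduce by exact binomial:

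- P(X ≥ 11 | n = 15, p = 0.5) = (1365 + 455 + 105 + 15 + 1) / 32768 = 1941 / 32768 = 0.0592 (stated 5.9%).
- P(X ≥ 11 | n = 15, p = 0.8) = 0.8358 (stated 83.6%).

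Neither figure involves the marker.

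**The case against.** The best defence is the narrow reading. The superscript follows the second alternative in the row title, and restricting only the substitute marker tracks the wording of 2.2.2. On that reading every expansion patient keeps CA 19-9 on Day 3 and at the safety visit. This stands as a plausible reading, so the loss in the expansion cohort is conditional on the literal one. It does not rescue the footnote, because epithelioid mesothelioma is still left out and the reader has to guess what the tag governs.

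A reader might infer that the signed-rank test will have no pairs at all. The documents do not support that. Section 10.4.9 says the changes will be determined, 3.1.3 and 10.3.3 tell staff that follow-up markers are needed, and LMB-100 is given at a single centre. What is absent on the literal reading is a scheduled value; a value may still be drawn.

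A reader might also infer that an escalation patient who is evaluable by CA 19-9 alone has no scheduled draw of that marker. Section 2.2.2 schedules one at screening, so only the follow-up draws are in question. This route does not reach the expansion cohort, where measurable disease is required.

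The dependence of other rules on the marker should not be overstated either. Section 6.3.2 says markers alone cannot establish response, and extension also requires no progression on CT and is at the investigator's discretion.

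**Conclusion.** The calendar contradicts the rest of the plan as written. On the literal reading, 0 of 15 expansion patients have a scheduled follow-up marker, and neither do escalation patients with pancreatic adenocarcinoma, extrahepatic cholangiocarcinoma or epithelioid mesothelioma. On the narrow reading the gap shrinks to epithelioid mesothelioma in escalation, plus an ambiguous footnote. Because the restriction fits the mesothelin row and several sections presume serial markers, a misplaced tag is the likeliest explanation.

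The consequence is limited to an exploratory analysis and to the provisions that lean on the marker. The primary endpoint, the sample size and the 11-of-15 rule are unaffected. The counts assume three completed cycles and attendance at the safety visit. It would be wrong to conclude that the marker analysis is lost, or that the trial's main conclusion is at risk.

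**What to change.** Remove footnote 5 from the tumour-marker row and keep it on the mesothelin-expression row. The existing Day 3 (or Day 4 before LMB-100) and safety-visit draws then apply to all patients with an appropriate marker. Mark Screening on that row to agree with 2.2.2. Each expansion patient completing three cycles would then have a screening value, one cycle 1 value before LMB-100, two later Day 3 values and one safety-visit value.

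If 10.4.9 is amended to define baseline, use the value taken before any study drug, which is the screening value. The cycle 1 Day 3 draw is unsuitable because tofacitinib starts on Day 1 and the objective in 1.1.3 concerns change with treatment.

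The cost is one footnote tag and one table cell in an amendment, plus a sentence if baseline is defined. Blood is already drawn for routine labs on Day 3 and at the safety visit, so no visit or venepuncture is added.

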3.5 CRITERIA FOR REMOVAL FROM PROTOCOL THERAPY AND OFF STUDY CRITERIA

Prior to removal from study, effort must be made to have all subjects complete a safety visit as indicated in the **Study Calendar** following the last dose of study therapy. Criteria for removal from protocol therapy

- Completion of study therapy
- Progressive disease
- Participant requests to be withdrawn from active therapy
- Pregnancy
- Unacceptable Toxicity as defined in Sections 3.1.1 and 3.3
- Requirement for any of the prohibited medications listed in Section 4.1.2
- Investigator discretion

3.5.1 Off-Study Criteria

- Completed study follow-up period
- Decision to end the study
- Participant requests to be withdrawn from study
- Death

4 CONCOMITANT MEDICATIONS/MEASURES

4.1.1 Permitted Therapy

Concomitant therapy includes any medication (e.g., prescription drugs, over-the-counter (OTC) drugs, approved dietary and herbal supplements, nutritional supplements) used by a participant from the screening period until the follow-up visit. If any treatment is given within 4 weeks prior to screening this should be reported to the investigator and recorded in the eCRF.

All therapy and/or medication administered to manage adverse events should be recorded on the Adverse Event eCRF.

4.1.2 **Prohibited Therapy**

Patients should be treated for all concomitant conditions and adverse events according to accepted standards of medical care at the discretion of the investigator. The following treatments are not permitted during the study:

- Any other investigational therapy
- Cytotoxic chemotherapy agents other than study agents
- Radiotherapy. Note: palliative radiotherapy is allowed.

- Strong inhibitors or inducers of CYP3A4 (as can be found here: **Flockhart Table** or in another frequently updated source)
- Any medications or treatments that may adversely affect the immune system such as allergy injections, immune globulin, interferon, immunomodulators, cytotoxic drugs, or systemic corticosteroids (oral or injectable) at doses higher than needed for adrenal replacement (except as specified as part of protocol treatment).
- Other systemic anti-neoplastic agents and targeted therapies
- Live vaccines

If any anti-neoplastic or investigational therapies listed above are needed, the patient will be considered to have evidence of progressive neoplastic disease and have experienced treatment failure with study treatment and should be withdrawn from study treatment.

All concomitant treatments must be documented in the eCRF.

5 BIOSPECIMEN COLLECTION

5.1 CORRELATIVE STUDIES FOR RESEARCH/PHARMACOKINETIC STUDIES

5.1.1 LMB-100 Pharmacokinetic Assessments

All blood samples for PK assessment will be collected from an IV line different to that receiving the infusion to measure free and total concentrations for LMB-100 for all patients. The pretreatment PK assessment may be drawn from the line that will be used to administer LMB-100. The date and time of each sample collection will be recorded. If multiple samples are drawn at a given time point, the PK sample should take precedence.

Free and total plasma concentrations of LMB-100 will be measured using validated ligand-binding assays.

